7.3.4. Safety Analysis

Adverse events will be summarised by treatment and severity. Separate tables summarising adverse events and their relationship to study treatment as well as summarising adverse events by treatment and timepoint will also be produced.

Serious adverse events will be listed and summarised by site, category and treatment. Separate tables will also be produced summarising serious adverse events and their relationship to study treatment as well as summarising serious adverse events by treatment and timepoint.

Vital Signs and Laboratory blood tests will be summarized by treatment per visit and will be presented as means and standard deviations if data is consistent with that from a normal population distribution, and as medians and inter-quartile ranges for data that is inconsistent. Categorical variables will be presented as frequencies and percentages.

If it is deemed appropriate, treatment effect will be assessed via t-test for continuous variables and Chi-square test or Fisher exact test for categorical variables (with the appropriate generalized linear model being used).

7.4. Exploratory Analysis

7.4.1. Exploratory Mechanistic Testing

Analysis to investigate any difference in effect of OC459 and placebo for the exploratory analyses below will be performed using the difference in values via unpaired (two-sample) t-test or Mann-Whitney U tests for non-parametric data.

- Changes in inflammatory cell counts by flow cytometry after drug treatment but before virus inoculation (for blood and nasal samples, not bronchial): Day -21 to Day -8.
- Changes in soluble mediators after drug treatment but before virus inoculation (nasal samples): Day -21 to Day 0.
- Changes in cell counts from bronchial biopsies taken at Day -8 and Day 5 will also be assessed CRTH2+ cells (cells/mm² tissue) & EG2+ activated eosinophils (cells/mm² tissue).

7.4.2. Exploratory Testing For Antiviral Response

Rhinovirus-induced IFN- β , λ 1 and λ 2/3 levels (protein and mRNA) will be measured in bronchial epithelial cell cultures stimulated with RV-16, RV-1B and Poly I:C after 6H, 24H and 48H. These will be compared across placebo and treatment groups, and to media and filtered virus stock controls.

Data will be presented in a summary table and will include mean and standard error. Statistical analysis will be carried out for multiple comparisons using ANOVA, or where non-parametric methods are required, Wilcoxon or Kruskal-Wallis testing. Differences will be considered significant at $P < 0.05$.

mRNA levels of a panel of interferon stimulated genes (MxA, RIG-I, OAS, viperin, IP-10, PKC) will also be analysed across the 3 timepoints using the same methods.

7.4.3. Exploratory Correlation Testing

We will correlate lower respiratory symptom scores with the ACQ (which reflects symptoms over the last 7 days) at two timepoints:

- ACQ-6 at day -9 vs sum of lower respiratory symptom scores day -15 to day -9 inclusive
- ACQ-6 at day 10 vs sum of lower respiratory symptom scores day 4 to day 10 inclusive

Potential relationships between the above will be investigated using Spearman’s rank correlations.

Potential relationships between outcome variables and antiviral response variables will be investigated using Spearman’s rank correlations. Tests will be carried out between the following:

Efficacy Analysis Variable
 
 • Lower respiratory symptom score (peak and AUC) • Upper respiratory symptom score (peak and AUC) • Virus load (peak and AUC) • Morning PEFr (peak decline) • Morning FEV₁ (peak decline) • FeNO (peak increase) • Any cytokine statistically induced by infection (peak increase) 	vs	
Antiviral Response Variable:
 
 • interferon levels (β, λ1, λ2/3) • mRNA levels of interferons (β, λ1, λ2/3) • mRNA levels of a panel of interferon-stimulated genes (MxA, RIG-I, OAS, viperin, IP-10, PKC)
--	----	---

7.4.4. Further Testing For Outcome Variables

In addition to the above exploratory tests, secondary outcome variables will be measured and analysed using alternative methods if deemed appropriate. Table 03 below contains a table showing the possible comparisons used:

Table 03: Potential Exploratory Analyses of Outcome Variables

Variable:	Comparison				
	Peak during infection (day 0 to 10)	Change from day 0 to peak infection	Area under curve during infection (day 0 to 10)	Total during infection (day 0 to 14)	Average value at each timepoint day 0 to 10
Lower respiratory symptom score ¹	X	X	N/A	X (primary outcome)	X
Upper respiratory symptom score ¹	X	X	N/A	X (secondary outcome)	X
Morning PEFR ²	X (peak fall)	X (secondary outcome)	X	N/A	X
Morning FEV ₁ ²	X (peak fall)	X (secondary outcome)	X	N/A	X
Clinic FEV ₁ ²	X (peak fall)	X (secondary outcome)	X	N/A	X
ACQ-6	(day 10)	X (secondary outcome)	N/A	N/A	N/A
PC ₂₀	(day 7)	X (secondary outcome)	N/A	N/A	(day -9 only)
FeNO	X	X (secondary outcome)	X	N/A	X
Blood eosinophils	X	X (secondary outcome)	N/A	N/A	X
Virus load	X (secondary outcome)	N/A	X	N/A	X
Soluble mediators - nasal ³	X	X (secondary mechanistic outcome)	X	N/A	X
Soluble mediators - bronchial ³	(day 5)	X (secondary mechanistic outcome)	N/A	N/A	(day -8 only)

Items marked as 'X' or with a specific study day are to be assessed as exploratory analyses

7.5. Missing Data and Withdrawn Subjects

Missing values for primary and secondary endpoints (as per Table 03), viral load and soluble mediators will be extrapolated for cumulative / area under the curve calculations.

Imputation will be based upon the values before and after the missing timepoint(s). Missing values will be derived using the following formula:

$$x_n = x_{(n-1)} + z$$

Where:

x_n = missing value at day 'n'

$x_{(n-1)}$ = last recorded value before missing data begins

z is a constant derived from the last recorded value $x_{(n-1)}$, the first value obtained after missing data y , and d = the number of missing data points between $x_{(n-1)}$ & y

$$z = \frac{y - x_{(n-1)}}{d + 1}$$

For example; if we are missing data at day 4 and we know that the value at day 3 is 1 and the value at day 5 is 3 then we can calculate constant z as $z = \frac{(3-1)}{(1+1)} = 1$ thus the missing value at day 4 would be: $x_4 = (x_3 + 1) = (1 + 1) = 2$.

Imputation and analysis involving missing and imputed data will be taken under the assumption that the data is missing-at-random (MAR).

If imputation has taken place, sensitivity analyses will be performed to ensure integrity of statistical testing based on extrapolated scores.

No other values for missing data will be imputed.

If there is a missing baseline value for virus load, the previous value (i.e. at randomisation / day - 21) will be taken (virus load should be below the lower limit of detection prior to inoculation). If there is a missing baseline value on another variable and after unblinding the subject is in the placebo group, the baseline will be replaced with a value from a previous visit (e.g. randomisation / day -21) if available. If after unblinding the subject is in the treatment group, the baseline will not be replaced (with the exception of virus load, as above).

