7.2. Primary Analysis

Uncorrected lower respiratory symptom scores collected from D0 to D14 will be aggregated to create an overall total for each patient. Where patient scores are missing, data will be imputed based upon rules set within Section 7.5. Patients missing $\geq 20\%$ of score data will be excluded from any additional per-protocol analyses.

Data will be presented using summary statistics per treatment group and will include median and interquartile range (IQR). A supplementary plot showing individual measurements for both groups with a box & whisker overlay showing median and IQR will be produced.

Primary analysis to test for difference between the mean aggregated scores of the two treatment groups will be carried out using Mann-Whitney U tests. Differences will be considered significant at $P < 0.05$. All P values are two-sided.

An additional secondary analysis will take place correcting the scores for bronchoscopy-related symptoms. Full methodology will be clarified within Section 7.3.1 below.

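### SAP 7.5 defines its gap-filling formula in two incompatible ways for gaps of two or more days, and counts data points rather than days for visit-based AUCs

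*SAP*

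**What the plan says.** SAP 7.2 sends missing primary scores to the imputation rule: "data will be imputed based upon rules set within Section 7.5". The primary endpoint (SAP 6.2) is the sum of 15 daily lower respiratory scores, each from 0 to 21, over Day 0 to Day 14.

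SAP 7.5 gives the rule. Missing values "will be extrapolated for cumulative / area under the curve calculations", and the section's wording covers more than one missing timepoint in a row. The formula is `x_n = x_(n-1) + z`, with these definitions:

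- `x_(n-1)` is the "last recorded value before missing data begins".
- "z is a constant derived from the last recorded value", from y (the first value after the gap) and from d: `z = (y − x_(n-1)) / (d + 1)`.
- d is "the number of missing data points between" the two recorded values.

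The single worked example begins "if we are missing data at day 4 and we know that the value at day 3 is 1". The value at Day 5 is 3, and Day 4 is filled as 2. The section promises sensitivity analyses if imputation takes place, without describing them, and adds "No other values for missing data will be imputed".

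**The concern.** The symbol `x_(n-1)` does two jobs. As a subscript in a recursion it should move forward one day at a time. By its verbal definition it stays at the last recorded value, and an imputed value is not a recorded one. A programmer who follows the definition fills a multi-day gap with one flat value. A programmer who follows the subscript interpolates linearly. The two give different primary totals from the same diary, and the example cannot tell them apart.

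A second, separate matter is that d counts data points and takes no account of elapsed days. That is harmless for a daily diary. It is not harmless for measurements taken at unequal intervals and then integrated by the linear trapezoid (SAP 7.6).

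What is at stake is one reproducible derivation of the primary total, and correctly placed values in the visit-based AUCs.

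**Working it through.** **The plan's own example.** x = 1, y = 3, d = 1, so z = (3 − 1)/(1 + 1) = 1 and Day 4 = 1 + 1 = 2. It reproduces under both readings.

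**General result for daily scores, gap inside Day 0 to 14.** Let x be the value before the gap, y the value after it, and z = (y − x)/(d + 1).

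- Literal reading, every missing day x + z: gap sum = d(x + z) = dx + d(y − x)/(d + 1).
- Linear reading, k-th missing day x + kz: gap sum = dx + z × d(d + 1)/2 = d(x + y)/2.
- Literal minus linear = −(y − x) × d(d − 1) / (2(d + 1)).

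The difference is zero when d = 1 or y = x. The literal reading is too low while symptoms rise and too high while they fall.

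**Illustrations.** The values of x, y and d are assumptions; the documents give none.

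| x → y | d | literal | linear | difference in sum |
|---|---|---|---|---|
| 2 → 8 | 2 | 4, 4 | 4, 6 | −2 |
| 2 → 8 | 3 | 3.5, 3.5, 3.5 | 3.5, 5, 6.5 | −4.5 |
| 8 → 2 | 3 | 6.5, 6.5, 6.5 | 6.5, 5, 3.5 | +4.5 |
| 2 → 14 | 3 | 5, 5, 5 | 5, 8, 11 | 15 − 24 = −9 |

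For the last row, one such subject in an arm of 15 moves the arm mean by 9/15 = 0.6 points.

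**Limits on gap length.** SAP 7.2 excludes subjects with 20% or more of scores missing (0.20 × 15 = 3 days), but only from per-protocol analyses. With two missing days the largest possible error is 21 × 2/6 = 7 points. The full analysis set (SAP 5.2) requires 14 days completed after inoculation and sets no limit on missing diary days. The arithmetic ceiling there, 13 missing days between scores of 0 and 21, is 21 × 156/28 = 117 points. That is a bound, not an expectation.

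**Unequal spacing.** Nasal samples after inoculation fall on Days 0, 2, 3, 4, 5, 7 and 10 (SAP 7.3.2 and 4.9). With one missing visit the formula always takes the midpoint (weight 0.5). If the neighbouring visits are on days a and c and the missing one is on day b, the time-based weight is w = (b − a)/(c − a). The trapezoid error over Day 0 to 10 is (0.5 − w) × (c − a)/2 × (y − x).

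| Missing day | Neighbours | w | AUC error |
|---|---|---|---|
| 2 | 0, 3 | 0.667 | −0.25 (y − x) |
| 3 | 2, 4 | 0.5 | 0 |
| 4 | 3, 5 | 0.5 | 0 |
| 5 | 4, 7 | 0.333 | +0.25 (y − x) |
| 7 | 5, 10 | 0.4 | +0.25 (y − x) |

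As an assumed example, take 5.0 on Day 5, 2.0 on Day 10 and Day 7 missing. The formula gives 5 + (2 − 5)/2 = 3.5; by study day it is 5 + 0.4 × (2 − 5) = 3.8. The Day 5 to 10 area is (5 + 3.5)/2 × 2 + (3.5 + 2)/2 × 3 = 16.75, against (5 + 2)/2 × 5 = 17.5. The shortfall is 0.75, or 4.3%. Because d = 1 here, the literal and recursive readings give the same misplaced value.

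**The case against.** The strongest reply is that this is loose notation and not a wrong method. A recursion with a constant step and a divisor of d + 1 is linear interpolation, and dividing by d + 1 has a purpose only if the step is applied d times. That is probably what was intended. It does not remove the conflict: to obtain interpolation, the same symbol must stay fixed inside z and move outside it, which the definition does not say.

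It can also be said that incomplete diaries should not reach the analysis, since Protocol 4.4 and 9.17 ask for complete cards to Day 14. The SAP relaxes this to 14 days completed and plans for imputation, so the rule will be used if gaps occur. The promised sensitivity analyses help only once the main rule is fixed.

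Four stronger readings are tempting, and the documents do not support them:

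- *The totals are wrong.* They are wrong only if the definition is coded literally and multi-day gaps occur. One-day gaps in daily data are exact.
- *The error is 41% of the planned effect.* 9/22.21 is 41%, but this sets one assumed subject's error against a difference between group means. On the mean of 15 it is 0.6/22.21 = 2.7%. The primary test is Mann-Whitney, so a single shift acts only through ranks. The rule is the same in both arms, and no bias between them is shown.
- *Unequal spacing distorts the primary score.* It cannot, because that score is daily.
- *A gap that reaches Day 14 has no later value and adds nothing to the sum.* Protocol 9.4 keeps the diary for six weeks after inoculation, and SAP 7.5 does not confine y to Day 14 or earlier. Only a diary that stops for good lacks y, and the plan nowhere says that unfilled days count as zero.

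The AUC point is also limited in reach. SAP 7.4.4 treats AUC comparisons as exploratory and makes peak virus load the secondary outcome. However, Protocol 3.1 lists the virus load AUC among the secondary outcomes, and SAP 7.3.3 uses AUCs in correlations.

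**Conclusion.** The point stands as a conflict between definition and formula in the derivation of the primary total, plus a separate fault in visit-based AUCs.

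For the primary score, the two readings differ by |y − x| × d(d − 1)/(2(d + 1)) per gap: nothing for one day, and 9 points for one subject in the assumed three-day rise from 2 to 14. The effect on the trial depends on how many multi-day gaps occur, how long they are, and whether they fall while symptoms rise or fall. None of this is known from the documents, so no effect on the treatment comparison can be claimed.

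For the visit-based AUCs, the misplacement follows from the definition of d whenever a value next to an unequal interval is missing. For a single missing nasal Day 2, 5 or 7 it is 0.25 × |y − x|; for Day 3 or 4 it is zero.

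**What to change.** In SAP 7.5, replace the formula with interpolation by study day:

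`x(t) = x(a) + (y − x(a)) × (t − t_a) / (t_y − t_a)`

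Here t is the study day of the missing value, a the last recorded timepoint (on day t_a), and t_y the day of the first value after the gap. For the daily diary this makes the k-th missing day x + kz, for k = 1 to d. For visit-based variables it places the value correctly between unequal visits.

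Add a worked example with a gap of at least two days, such as 2 to 14 over three missing days, giving 5, 8 and 11.

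State that diary scores recorded after Day 14 may serve as y for a gap that includes Day 14. Scaling a short total up by 15 over the number of days observed is not a good substitute. It ignores the later scores that the diary collects, and it gives the late days the subject's average even though SAP Table 03 looks for the peak in Day 0 to 10.

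The cost is a change of SAP wording and one line of code. No new data are needed.

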9 ASSESSMENT AND FOLLOW-UP

9.1 SUMMARY OF STUDY ASSESSMENTS AND PROCEDURES

After screening and providing informed consent, eligible participants will undergo baseline investigations and randomisation, followed by a 21 day run-in period on placebo or OC459. Towards the end of this period they will have a baseline bronchoscopy and other investigations. At the end of the run-in period, subjects will have a further set of investigations prior to rhinovirus inoculation the same day. Regular sampling and assessments will take place as indicated whilst treatment administration continues uninterrupted for a further 14 days, for a total of 5 consecutive treatment weeks. Trial medications are then stopped (day 14). Subjects will attend for a final follow-up visit 4 weeks later with convalescence investigations (day 42). Table 1 summarises subject visits and procedures during the study. Details of the individual study procedures are listed below.

Study participants will be seen frequently during the study period, daily if they wish. They have details to contact the Clinical Research Fellow and Clinical Research Nurse, and will be offered daily telephone contact. In this way participants will be assessed regularly by the investigating team and any adverse events detected rapidly. When the study is completed, subjects will return to the care of their GP (they will not be routinely followed-up by the study group).

	Screening visit 1	Screening visit 2	Visit 1 (baseline)	Visit 2	Visit 3	Visit 4	Visit 5	Visit 6	Visit 7	Visit 8	Visit 9	Visit 10	Visit 11
Study day			-21	-9	-8	0	2	3	4	5	7	10	42
Ideal weekday			F	W	T	F	Su	M	T	W	F	M	F
Visit length	30 min	60 min	60 min	45 min	3 hr	60 min	45 min	45 min	45 min	3 hr	60 min	45 min	30 min
Skin prick test	X												
Viral serology	X												X
Asthma Control Questionnaire (ACQ)	X		X	X		X						X	X
Spirometry (in clinic)	X		X	X		X	X	X	X	X	X	X	X
Histamine challenge (PC ₂₀)		X	X	X							X		
Exhaled nitric oxide (FeNO)		X	X	X		X		X		X	X	X	X
Blood tests		X	X		X			X		X		X	X
ECG		X											
Urine pregnancy test		X											
Chest radiograph		X											
IMP or placebo administration			Daily from day -21 → day 14 (then stop)										
Nasosorption			X			X	X	X	X	X	X	X	
Nasal lavage			X			X	X	X	X	X	X	X	
Nasal scrape			X		X			X		X			
Bronchoscopy (bronchosorption, BAL, brushings, biopsies)					X					X			
Sputum induction			X	X					X		X		
Virus inoculation						X							

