4.10. Study Baseline

For Primary and Secondary endpoint assessments, baseline will be determined as the last measurement taken prior to virus inoculation i.e. Day 0 (ACQ-6, home PEFR, home FEV1, clinic FEV1, clinic FVC, FeNO, virus load, soluble mediators) where available. If/where this is missing, the value on the previous visit will be used, for example, laboratory bloods and PC20 (for laboratory bloods, the sample on day -8 will be taken as a baseline, for PC20, the result from day -9 will be taken).

Demographic baseline variables will be taken at Screening, Day -21 and Day 0 (where available).

5. Analysis Sets

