7.3. Secondary Analysis

7.3.1. Secondary Efficacy Analysis

Lower respiratory symptom scores collected from D0 to D14 will be corrected for the effects of bronchoscopy by subtracting the baseline symptoms value (mean average of values from D-13 to D-9) from the two days affected by bronchoscopy symptoms (day -8 and day -7). The adjusted residual symptom scores for day -8 and day -7 (which we assume to be purely bronchoscopy related) would then be subtracted from day 5 and day 6 to complete the correction.

Analysis to test for difference between the mean aggregated corrected scores of the two treatment groups will be carried out using Mann-Whitney U tests.

The effect of the drug on asthma exacerbations (as defined by change from day 0 to peak infection in symptoms, lung function, and measures of lung inflammation) will be using presented summary statistics per treatment group and will include median and interquartile range (IQR). Within-subject differences will be analysed using ANOVA and 2-tailed paired Student's t-tests or Wilcoxon signed rank test in the event where data is not consistent with a normal population distribution. Analysis to determine the difference in effect of OC459 and placebo will be performed using unpaired (two-sample) t-test or Mann-Whitney U tests for data not consistent with a normal population distribution at each phase of the study.

Differences will be considered significant at $P < 0.05$ within a hierarchy of the primary outcome, and interpreted more cautiously for secondary efficacy outcomes, (likewise more so for

exploratory outcomes). Patients missing $\geq 20\%$ of endpoint data will be excluded from any additional per-protocol analyses. Analyses that are conducted using the Per Protocol analysis set that are in agreement with conclusions derived from the Full analysis set will be more strongly interpreted than those in disagreement. All P values are two-sided.

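### A missing baseline is replaced for placebo subjects but not for OC459 subjects, after unblinding, so the secondary change-from-baseline comparisons treat the arms differently

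*SAP*

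**What the plan says.** SAP 7.5 (Missing Data and Withdrawn Subjects) sets three rules for a missing baseline.

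- Virus load, either arm: "If there is a missing baseline value for virus load, the previous value (i.e. at randomisation / day - 21) will be taken".
- Any other variable, placebo: "If there is a missing baseline value on another variable and after unblinding the subject is in the placebo group", then "the baseline will be replaced with a value from a previous visit (e.g. randomisation / day -21) if available".
- Any other variable, OC459: "If after unblinding the subject is in the treatment group, the baseline will not be replaced".

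SAP 4.10 (Study Baseline) takes Day 0 as baseline for ACQ-6, home PEFR and FEV1, clinic FEV1 and FVC, FeNO, virus load and soluble mediators. It then adds "If/where this is missing, the value on the previous visit will be used", citing laboratory bloods (Day -8) and PC20 (Day -9). It mentions neither arm nor unblinding.

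The baseline is needed in SAP 7.3.1, where the effect on exacerbations is "as defined by change from day 0 to peak infection in symptoms, lung function, and measures of lung inflammation". Table 03 in SAP 7.4.4 marks that change as the secondary outcome for morning PEFR, morning and clinic FEV1, ACQ-6, PC20, FeNO and blood eosinophils.

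**The concern.** A data-handling rule that differs by allocation breaks the symmetry that randomisation provides. Under SAP 7.5 the OC459 arm becomes a complete-case sample. The placebo arm mixes changes measured from the scheduled baseline with changes measured from an earlier visit. Any average movement during the run-in then enters one arm's mean only, and any selection caused by excluding subjects acts on the other arm only.

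The rule also runs only once allocation is known. SAP 5.3 sets a different standard for major protocol deviations, which are to be defined before database lock and without knowledge of treatment.

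If 4.10 and 7.5 stay as they are, two analysts could follow the SAP faithfully and report different secondary results.

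**Working it through.** **1. Denominator.** The documents' only design figure is 15 evaluable subjects per arm (Protocol 10.1, SAP 4.4). Reading 22.21 as the raw difference and 21.15 as the SD gives 22.21/21.15 = 1.05. The normal formula is n = 2 × (1.960 + 0.842)² / 1.05² = 15.70/1.103 = 14.2, rounded up to 15. This reproduces the plan's figure. It is used below only as the arm size.

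**2. Which analyses are exposed.**

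- Primary endpoint (SAP 6.2): no baseline is subtracted, so it is not exposed.
- Virus load: replaced in both arms, and Table 03 marks its change from Day 0 as not applicable. Not exposed.
- Bronchial mediators: no bronchoscopy before Day -8, so there is nothing to borrow in either arm.
- Nasal mediators: SAP 7.3.2 takes change from Day -21 in both arms. They are exposed only under the Day 0 baseline of 4.10 and Table 03.
- ACQ-6, home PEFR and FEV1, clinic FEV1, FeNO, PC20 and blood eosinophils: exposed.

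**3. Bias.** Let m of 15 baselines be missing per arm, and let D be the mean Day -21 to Day 0 drift, equal in both arms (no drug effect). A placebo change measured from Day -21 equals the Day 0 change plus the run-in movement, so its expectation rises by D. OC459 subjects with a missing baseline drop out. Hence

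bias (OC459 minus placebo) = −(m/15) × D.

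The documents give neither m nor D. The values below are assumptions, with D in SD units.

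| m | Analysed, OC459 v placebo | D = 0 | D = 0.5 | D = 1.0 |
|---|---|---|---|---|
| 1 | 14 v 15 | 0 | −0.03 | −0.07 |
| 3 | 12 v 15 | 0 | −0.10 | −0.20 |
| 5 | 10 v 15 | 0 | −0.17 | −0.33 |

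For example, m = 3 and D = 0.5 gives −(3/15) × 0.5 = −0.10. The direction follows the drift: deterioration over the run-in enlarges the placebo worsening and flatters OC459, and improvement does the reverse.

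**4. Type I error.** Each case was simulated 5,000 times under no drug effect, using a two-sample t-test, baselines missing at random and an assumed between-visit correlation of 0.6.

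| m | D = 0 | D = 0.5 | D = 1.0 |
|---|---|---|---|
| 1 | 5.3% | 5.2% | 5.2% |
| 3 | 4.6% | 5.6% | 7.1% |
| 5 | 4.3% | 6.8% | 10.9% |

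Simulated biases agreed with the formula to within about 0.01 SD.

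**5. One rule for both arms.** Under the same assumptions, leaving baselines missing in both arms gave bias within about 0.01 SD of zero and type I error of 4.6% to 5.5%. Replacing in both arms also removed the bias, with type I error of 2.5% to 5.0%.

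**6. Is an arm-neutral substitute available?** Treatment starts at Day -21, "followed by a 21 day run-in period on placebo or OC459" (Protocol 9.1). The visit schedule has ACQ, clinic spirometry and FeNO at Day -9, and home spirometry daily. All are on-treatment values in both arms. PC20 (baseline Day -9) and blood eosinophils (baseline Day -8) have only pre-treatment values before their baselines.

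**The case against.** The best defence is that Day -21 precedes treatment. For an OC459 subject it cannot stand in for an on-treatment Day 0, whereas for a placebo subject it arguably can. The SAP does not state this reason, but it is sensible. It is an argument against using Day -21 in the OC459 arm. It does not justify a rule that differs by arm, because Day -9 and diary values serve both arms for most variables, and elsewhere the baseline can be left missing in both.

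Other parts of the defence stand and limit the point.

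- The full analysis set requires inoculation at Day 0, and the protocol places that day's investigations before inoculation. A missing clinic baseline therefore needs an omitted or failed test, so numbers may be small.
- SAP 4.10 need not be a flat contradiction. It can be read as defining the scheduled baseline, or as a first fallback to Day -9 with 7.5 applying only if that is also missing. On the second reading 7.5 would rarely apply to ACQ-6, FeNO or clinic FEV1. The SAP does not say which reading is meant.
- The direction of the rule is prespecified. Only the choice of earlier visit is left open after unblinding.
- Secondary outcomes are to be interpreted more cautiously (SAP 7.3.1).

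A reader might also infer that the placebo arm keeps every subject. It does not, because replacement depends on an earlier value existing. Nor is lost power the defect. The planning difference of 1.05 SD belongs to the primary endpoint, and the documents give no effect size or SD for the exposed outcomes. Leaving baselines missing in both arms would give fewer subjects still (12 v 12 rather than 12 v 15 when m = 3).

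**Conclusion.** The rule is wrong as written and should be fixed for the secondary endpoints. The asymmetry is explicit in SAP 7.5 and does not depend on any assumption, and its relation to 4.10 is unresolved. The sensitivity analyses promised in 7.5 concern extrapolated scores and do not clearly cover replaced baselines.

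The size is conditional. It runs from no mean bias without drift to 0.33 SD, with type I error of about 11%, if 5 of 15 baselines per arm are missing and the drift is 1.0 SD. With 1 of 15 missing and 0.5 SD drift it is 0.03 SD. These figures assume that baselines are missing at random. Selection from excluding OC459 subjects alone would come on top and cannot be quantified from the documents.

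A reader might conclude that the trial's main result is compromised, or that the secondary comparisons are certainly biased. The documents support neither. The primary endpoint uses no baseline, and bias in the secondary comparisons needs both missing baselines and either drift or informative missingness.

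**What to change.** Delete the two allocation-dependent sentences in SAP 7.5. State one rule for both arms, fixed blind before database lock, and align 4.10 with it.

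- ACQ-6, clinic spirometry and FeNO: use the on-treatment Day -9 value.
- Home PEFR and FEV1: use the last diary day before Day 0.
- Variables with only pre-treatment values before their baseline (PC20, blood eosinophils, and nasal mediators in any analysis with a Day 0 baseline): leave the baseline missing in both arms. Substitute the earlier value in both arms as a sensitivity analysis.
- Nasal-mediator change in 7.3.2: keep the Day -21 baseline specified there, and reconcile 7.3.2 with 4.10 and Table 03, which use Day 0.
- Virus load: no change needed, since both arms are already treated alike.

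Deleting the 7.5 sentences alone is not enough. The 4.10 fallback would then give OC459 subjects a pre-treatment baseline for PC20 and blood eosinophils.

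The cost is SAP wording, with no new data, and a slightly smaller n where baselines stay missing. The change must be made before unblinding, because afterwards any choice between 4.10 and 7.5 is made with allocation known.
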